## 6.2 Rationale

CD HORIZON® Fenestrated Screw Spinal System has been CE-marked since 2011, for the treatment of degenerative disc disease (defined as back pain of discogenic origin with degeneration of the disc confirmed by history and radiographic studies), ankylosing spondylitis, spondylolisthesis, trauma (fracture or dislocation), spinal stenosis, curvatures (i.e., scoliosis, kyphosis or lordosis), tumor, pseudoarthrosis, revision surgery and/or failed previous fusion.

The CD HORIZON® Fenestrated Screw Spinal System with Fenestrated Screw Cement is designed to enhance the fixation strength of instrumentation in vertebrae with compromised bone quality. Currently, in the US, these screws with Fenestrated Screw Cement are 510(k) cleared only for the treatment of advance stage tumor subjects. However, within the US, nearly 50% of the population of subjects requiring spinal immobilization/stabilization procedures for degenerative disc disease, spondylolisthesis, trauma (fracture or dislocation), or spinal stenosis, also have compromised bone quality. Outside of the United States, the CD HORIZON® Fenestrated Screw Spinal System is CE-marked for broader indications and is being used to treat subjects with compromised bone quality. The proposed study design provides an opportunity to collect real-world clinical and radiographic data for CD HORIZON® Fenestrated Screw Spinal System with Fenestrated Screw Spinal System with Fenestrated Screw Spinal System of CD HORIZON® Fenestrated Screw Spinal System with Fenestrated Screw Spinal System with Fenestrated Screw Spinal System States for CD HORIZON® Fenestrated Screw Spinal System with Fenestrated Screw Spinal System States for CD HORIZON® Fenestrated Screw Spinal System States States Spinal States States Spinal System States S

The proposed primary endpoint at 12 months is sufficient to demonstrate improvement in disability (ODI). Furthermore, literature [21, 22] and previous Medtronic sponsored studies have demonstrated that subject reported outcomes at 12 months are consistent with outcomes reported at longer follow-up intervals. To confirm this, we will also be collecting patient reported clinical outcomes at 24 months. In addition, the proposed radiographic evaluation of the pedicle screws at 12 months is sufficient time to reveal any apparent evidence of implant loosening.

To assess long-term safety of the device, subjects will be followed-up for 24 months to collect safety information.

# 7. Product Description

## 7.1 General

The figure below shows the CD HORIZON® Legacy™ and Solera™ Fenestrated Screw

Figure 1: CD HORIZON® Legacy™(left) and Solera™(right) Fenestrated Screw

Medtronic Confidential

This document is electronically controlled

056-F275, v3.0 Clinical Investigation Plan Template

#MDT17040SD1703

Version 2.0/ 19 SEP 2018

The CD HORIZON® Legacy™ and Solera™ Fenestrated Screw Spinal System consists of a variety of cannulated screws with a series of fenestrations to allow polymethylmethacrylate (PMMA) bone cement (Fenestrated Screw Cement) to be injected into the treated site. The Fenestrated Screw Cement is used to augment screw fixation in subjects with compromised bone quality.

The CD HORIZON® Legacy™ Fenestrated Screws are specifically designed to connect to Ø 5.5mm rods and associated components contained within the CD HORIZON® Spinal System. The CD HORIZON® Solera™ Fenestrated Screws are specifically designed to connect to rods of Ø 4.75, 5.5 and 6.0mm and associated components contained within the CD HORIZON® Spinal System.

The CD HORIZON® Spinal System consists of a variety of rods, hooks, screws, plates, and other connecting components used to build a spinal construct. The entire spinal construct must contain CD Horizon® Spinal System components with at least one Fenestrated Screw cemented with Fenestrated Screw Cement.

Instrumentation is also available to facilitate implantation of these components. Additionally, other commercially available ancillary devices, implants, instrumentation and bone grafts/substitutes can be used during the surgery procedure.

All devices used in this study, shall be used within their intended use as described in the Instructions for Use for which CE mark has been obtained. Labeling of the devices will be in the appropriate local language. It is an investigator's responsibility to only use commercially available devices within intended use in the scope of this study.

The CD Horizon® Legacy™ Fenestrated Screws are fabricated from medical-grade titanium and/or medical grade titanium alloy. The CD HORIZON® Solera™ Fenestrated Screws are fabricated from medical-grade titanium and/or medical grade titanium alloy and/or medical grade cobalt-chromium-molybdenum alloy.

Fenestrated Screw Cement (Reference Number 7480724) is a polymethylmethacrylate (PMMA) that contains approximately 30% barium sulfate.

#### Nominal Composition of Fenestrated Screw Cement (Reference Number 7480724):

(Actual weight percentages of individual components will vary within accepted ranges)

POWDER (20 g of sterile powder in a packet)	LIQUID (9.0 g of sterile liquid in a vial)
Methylmethacrylate-styrene-copolymer 68.0% w/w	Methylmethacrylate (monomer) 99.1% w/w
Barium sulfate 30.0% w/w	N, N-dimethyl-p-toluidine 0.9% w/w
Benzoyl peroxide 2.0% w/w	Hydroquinone 75 ppm

The CD Horizon® Legacy™ and Solera™ Fenestrated Screws and the Fenestrated Screw Cement do not incorporate, as an integral part, a substance or human blood derivative referred to in Section 7.4 of Annex I (93/42/EEC).

For the manufacturing of the CD HORIZON® Legacy™ and Solera™ Fenestrated Screw and the Fenestrated Screw Cement no tissues of animal origin as referred to in Directive 2003/32/EC were used.

## 7.2 Dosage Form and Route of Administration

The operating surgeon should refer to the Instructions for Use (IFU) for the CD Horizon® Legacy™ and Solera™ Fenestrated Screws and the Fenestrated Screw cement for Warnings, Precautions, and Operative Steps on the usage of the products. The recommended amount of cement to be injected is also specified in the IFU.

## 7.4 Packaging

The CD HORIZON® Fenestrated Screw Spinal System is provided in a set and must be sterilized by the hospital prior to use. The product can be steam-sterilized using process parameters listed in the indication for use.

The Fenestrated Screw Cement is provided sterile and is intended for single use only. The powder and package are sterilized with gamma radiation. The liquid is sterilized using filtration and is contained in a glass vial. The outside of the glass vial is sterilized with ethylene oxide gas. Once the seal on the sterile package has been broken, the product should not be re-sterilized or reused. Labelling is specific to the geography and in accordance with local regulations.

## 7.5 Intended Population

The CD HORIZON® Fenestrated Screws, when used in conjunction with Fenestrated Screw Cement are intended to provide enhanced pedicular fixation in the treatment of subjects with compromised bone quality for the following indications:

CD HORIZON® Legacy™ Fenestrated Screw Spinal System: degenerative disc disease (defined as back pain of discogenic origin with degeneration of the disc confirmed by history and radiographic studies); ankylosing spondylitis, spondylolisthesis, trauma (i.e. fracture and/or dislocation), spinal stenosis, failed

FNS Study - Clinical			
#MDT17040SD1703	Version 2.0/ 19 SEP 2018	Page 22 of 65	Mecttronic

previous fusion (pseudoarthrosis), deformity (e.g. adult degenerative deformity, scoliosis, kyphosis, lordosis), revision surgery, and/or tumor.

CD HORIZON® Solera™ Fenestrated Screw Spinal System: degenerative disc disease (defined as back pain of discogenic origin with degeneration of the disc confirmed by history and radiographic studies), spondylolisthesis, trauma (i.e. fracture or dislocation), spinal stenosis, curvatures (i.e., scoliosis, kyphosis, or lordosis), tumor, pseudarthrosis, and/or failed previous fusion.

## 7.6 Product Use

The CD HORIZON® Legacy™ Fenestrated Screw Spinal System, the CD HORIZON® Solera™ Fenestrated Screw Spinal System, and the Fenestrated Screw Cement will be used according to the surgical techniques described in the CD HORIZON® Fenestrated Screw Spinal System Surgical Technique Brochures. The operating surgeon should refer to the respective products' IFU for any corresponding product information prior to using the product.

## 7.7 Product Training Requirements

The Investigator shall be experienced in the field of application and trained in the use of the study device(s), and qualified by education, training, and experience to assume responsibility for the proper conduct of the clinical investigation. Investigator qualifications will be verified by Curriculum Vitae (CV), and during Site Qualification Visits (SQVs), if applicable.

## 7.8 Product Receipt and Tracking

This is a post-market study and the CD HORIZON® Legacy™ Fenestrated Screw Spinal System, CD HORIZON® Solera™ Fenestrated Screw Spinal System, and the Fenestrated Screw Cement used during the study are commercially available. Product receipt and tracking is not required as the devices used during the study are purchased through normal commercial channels.

## 7.9 Product Storage

Products should be stored per the institutions' standard procedures.

## 7.10 Product Return

Products should be disposed of or returned per the institutions' standard procedures.

#MDT17040SD1703

Version 2.0/ 19 SEP 2018

Page 23 of 65

## 7.11 Product Accountability

Product accountability is not required for this post-market study as the devices used during the study are purchased through normal commercial channels and maintained per the institutions' standard procedures.

# 8. Selection of Subjects

## 8.1 Study Population

The study population are subjects with compromised bone quality seeking treatment at a participating study center for one or more of the following conditions:

- Degenerative Spinal Disease (e.g. degenerative disc disease, spondylolisthesis and/or spinal stenosis)
- Deformity (e.g. degenerative deformity)

Participating centers will be instructed to consecutively screen all subjects who are planned to undergo a procedure with an instrumented, posterior thoracic and/or lumbar spinal stabilization/immobilization using CD HORIZON® Fenestrated Screw Spinal System with Fenestrated Screw Cement against the eligibility criteria. Every effort will be made to enroll subjects in a consecutive manner.

Overall 100 subjects, with around 50 subjects (no less than 48 subjects) in each indication subgroup, that meet eligibility and provide written informed consent will be enrolled into this study. Subjects will be enrolled in approximately 10 centers in Europe.

The enrollment limit has been defined to be 50 patients per indication (degenerative spinal disease or deformity). Investigators will be requested to stop enrollment for a particular indication when the maximum enrollment (50 patients) for that indication has been reached.

A minimum of 1 subject and a maximum of 25 subjects will be included per site. For each site, no more than approximately 15 patients are allowed to be included per subgroup (degenerative spinal disease, deformity). These limits may be subject to change during the course of the study and will be communicated as appropriate to the Investigators, EC/IRB and regulatory authority, if required.

## 8.2 Subject Enrollment

Subjects planning to undergo a procedure with an instrumented, posterior thoracic and/or lumbar spinal stabilization/immobilization using CD HORIZON® Fenestrated Screw Spinal System with Fenestrated Screw Cement will be screened for eligibility to participate in the study. Subjects will be considered enrolled in the study once the informed consent form is signed; however, those who do not meet the

baseline inclusion/exclusion criteria or who do not undergo the fenestrated screw procedure as defined in this protocol will be exited from the study but can be replaced if enrollment is still open.

## 8.3 Inclusion Criteria

A subject must meet the following inclusion criteria to participate in this trial:

- 1. One or more of the following diagnostic indications:
  - Degenerative Spinal Disease (e.g. degenerative disc disease, spondylolisthesis and/or spinal stenosis)
  - Deformity (e.g. degenerative deformity)
- 2. Degenerative Spinal Disease patients only: Patient has been unresponsive to non-operative treatment for at least three months or has progressive symptoms or signs of nerve root/spinal cord compression while undergoing continued non-operative management.
- 3. Compromised bone quality defined as a hip DXA scan T-score less than or equal to -1.0 or spine quantitative CT (qCT) actual volumetric bone mineral density threshold of  $\leq$  120 mg/cm^3.
- 4. Requires a procedure with an instrumented, posterior thoracic and/or lumbar spinal stabilization and/or immobilization.
- 5. Is scheduled to receive a construct using CD Horizon® Spinal System components with at least one Fenestrated Screw cemented with Fenestrated Screw Cement.
- 6. At least 22 years old or greater at the time of informed consent.
- 7. Is able to understand and willing to sign the Patient Informed Consent Form.
- 8. Is willing and able to undergo the study procedure and perform the follow up visits.

## 8.4 Exclusion Criteria

A subject will be excluded from participating in this trial for any of the following reasons:

- 1. Has undergone stabilization and/or fusion procedure at the index or adjacent levels.
- 2. Will undergo vertebroplasty or kyphoplasty procedure during surgery.
- 3. Has been diagnosed with cauda equina syndrome.
- 4. Has been previously diagnosed with clinically significant peripheral neuropathy.

- 5. Has any degree of permanent neurologic deficit due to the presenting spinal disease (e.g. drop foot or gait deficit).
- 6. Has obesity defined by BMI greater than or equal to 35kg/m^2.
- Has documented allergy to the materials that will be used in the surgical or any imaging procedure (e.g. titanium alloys, cobalt-chromium-molybdenum alloys, PMMA Fenestrated Screw Cement, contrast medium)
- 8. Has overt or active bacterial infection, local or systemic, and/or potential for bacteremia.
- 9. Has a non-correctable spontaneous or therapeutic coagulation disorder or history of coagulation disorder associated with bleeding.
- 10. Has evolutive cardiac disease (e.g. symptomatic congestive heart failure, unstable angina pectoris, cardiac arrhythmia) nonreactive to medical treatment.
- 11. Has any disease (e.g., neuromuscular disease, etc.) that would preclude the potential benefit and/or accurate clinical evaluation of the safety of the spinal implant surgery.
- 12. Is pregnant or planning to become pregnant during the study duration.
- 13. Is illiterate or considered vulnerable as per the Investigator's assessment (e.g., participants incapable of judgment, or participants under tutelage).
- 14. Concurrent participation in another clinical study that may add additional safety risks and/or confound study results\*.

\*Subjects in concurrent studies can only be enrolled with permission from Medtronic. Please contact Medtronic's study manager to determine if the subject can be enrolled in the FNS Study.

## 9. Study Procedures

## 9.1 Schedule of Events

The study schedule, procedures, and methods of assessment are defined in detail to enable compliance with the required activities, and to ensure that the resulting data meet the criteria for evaluability. See Table 9-1 for visit schedule. The relevant electronic Case Report Forms (eCRFs) along with the applicable source documentation will be completed for each subject.

#MDT17040SD1703

Version 2.0/ 19 SEP 2018

Page 26 of 65

	Enrollment / Baseline	Surgery 	Prior to discharge	3 months (-1,5 / +3 months)	12 months (±3 months)	24 months (±6 months)
Informed consent	X 					
Demographics	х					
Medical History	х					
Hip DXA scan or spine qCT	X 					
Surgery Indication	х					
Surgery		Х				
Intraoperative cement extravasation/leakage		Х				
X-ray or CT scan			(X) 		х	(X) 

#### Table 9-1: Schedule of Events

<sup>1 The surgery procedure should occur as soon as possible after baseline but no later than 6 months after the date of acquiring the X-ray, MRI and/or CT-scan images. However, if the surgery cannot be done within 6 months after the date of the images then new images should be obtained.

<sup>2 Patient Informed Consent must be obtained prior to performing any study specific procedure.

<sup>3 Hip DEXA scan or spine qCT can be collected prior to enrollment/baseline visit if this is part of the standard of care and if it is not older than 3 months before the baseline visit. If not standard of care at the site, this is considered a study procedure and Patient Informed Consent must be obtained first.

<sup>4 It is at the Investigator's discretion to do a post-operative CT to assess pulmonary embolism in case there is a possibility for cement extravasation/leakage.

<sup>5 CT-scan or X-rays is required at 12 months follow-up for assessment of fusion (for those subjects where fusion is intended) and confirmation of stabilization of the pedicle screw instrumentation. If no fusion is observed at 1-year follow-up, it will be at the discretion of the Investigator to follow-up if fusion can be observed at 24 months (only if standard of care at the site). In case the patient is symptomatic at 24 months and receives a CT-scan or X-ray, stabilization of pedicle screw instrumentation and fusion status (for those subjects where fusion is intended) will be assessed.

#MDT17040SD1703

Version 2.0/ 19 SEP 2018

Page 27 of 65

	Enrollment / Baseline	Surgery 	Prior to discharge	3 months (-1,5 / +3 months)	12 months (±3 months)	24 months (±6 months)
Spinopelvic alignment 	х		(X) 		х	(X) 
Medication	х		х	Х	х	х
Neurological status	х				х	
VAS (back and leg pain)	х			Х	Х	Х
ODI	х			Х	Х	Х
EQ-5D 5L	х			Х	Х	Х
Adverse Events and/or device deficiencies		х	х	Х	Х	х
Protocol Deviations	х	Х	х	Х	Х	Х

## 9.1.1 Enrollment

All subjects must give their informed consent in accordance with the informed consent regulations per geographic region. At this visit, the following is a list of likely procedures:

- The subject will be presented with information about the clinical study and asked if he/she would like to participate
- The subject will be evaluated for eligibility per the inclusion/exclusion criteria.

If the subject meets the eligibility criteria and agrees to participate in the study, he/she will be asked to sign the patient informed consent (PIC). Once the PIC is signed, a copy of the signed PIC will be provided to the subject.

All subjects must sign the PIC prior to the collection of any study data. A subject is considered enrolled in this study at the time he/she signs the PIC. The subject will be assigned a unique, sequential code linked

<sup>6 Spinopelvic alignment parameters are only required to be assessed for deformity subjects.

<sup>7 Spinopelvic alignment parameters will only be collected prior to discharge in those sites where it is standard of care.

<sup>8 In case the patient is symptomatic at 24 months and receives a standing, frontal and sagittal full spine X-ray (at least C7 + femoral head must be visible), spinopelvic parameters will be assessed.

# FNS Study - Clinical Investigation Plan Image: Clinical Investigation Plan #MDT17040SD1703 Version 2.0/19 SEP 2018 Page 28 of 65 Medtronic

to their name, alternative subject identification or contact information. The Investigator will maintain a log of all subjects enrolled in the study.

The enrollment limit has been defined to be 50 patients per indication (degenerative spinal disease or deformity). Investigators will be requested to stop enrollment for a particular indication when the maximum enrollment (50 patients) for that indication has been reached. A minimum of 1 subject and a maximum of 25 subjects will be included per site. For each site, no more than approximately 15 patients are allowed to be included per subgroup (degenerative spinal disease, deformity). These limits may be subject to change during the course of the study and will be communicated as appropriate to the Investigators, EC/IRB and regulatory authority, if required.

## 9.1.2 Baseline

The following information will be collected at the baseline visit:

- Verification of Inclusion/Exclusion criteria
- Demographics
- Medical History
- Hip DXA scan or spine qCT (can be collected prior to baseline visit if this is part of the standard of care and if it is not older than 3 months before the baseline visit)
- Surgery Indication
- Imaging (X-ray, MRI and/or CT-scan) (can be collected prior to baseline visit if it is not older than 6 months before surgery date)
- Spinopelvic alignment parameters (only required for deformity subjects)
- Medication
- Neurological status
- VAS back and leg pain
- ODI
- EQ-5D 5L
- Protocol Deviations

#### 9.1.3 Surgery

The surgery procedure should occur as soon as possible after baseline but no later than 6 months after the date of acquiring the X-ray, MRI and/or CT-scan images. However, if the surgery cannot be done within 6 months after the date of the images then new images should be obtained.

The following information will be collected during surgery:

• Surgery procedure data

#MDT17040SD1703

Version 2.0/ 19 SEP 2018

Page 29 of 65

- Surgery time
- Blood loss and Transfusion
- Intraoperative cement extravasation/leakage
- Device Models
- Adverse Events and/or device deficiencies
- Protocol Deviations

It is recognized that the situation of a subject might change after enrollment. Due to Investigator's discretion, a subject might not receive at least one Fenestrated Screw cemented with Fenestrated Screw Cement during the procedure. If this situation occurs this shall be documented on a study deviation eCRF, including rationale for change in procedure and the study early termination form will be completed in the eCRF.

#### 9.1.4 Postoperative assessment prior to hospital discharge

The following information will be collected prior to hospital discharge:

- Spinopelvic alignment parameters (only required for deformity subjects in those sites where it is standard of care)
- Medication
- Adverse Events and/or device deficiencies
- Protocol Deviations

It is at the Investigator's discretion to do a post-operative CT to assess pulmonary embolism in case there is a possibility for intraoperative cement extravasation/leakage.

# 9.1.5 Postoperative assessment at 3 months (-1,5/+3 months), 12 months (±3 months) and 24 months (±6 months)

The following information will be collected at the post-operative visits:

- Medication
- VAS back and leg pain
- ODI
- EQ-5D 5L
- Adverse Events and/or Device Deficiencies
- Protocol deviations

# FNS Study - Clinical Investigation Plan Image: Study - Clinical Investigation Plan #MDT17040SD1703 Version 2.0/19 SEP 2018 Page 30 of 65 Medtronic

The post-operative assessment at 12 months also includes

- An evaluation of neurological status
- A radiologic evaluation of:
  - Pedicle screw instrumentation stabilization
  - Fusion status for those subjects where fusion is intended (if no fusion is observed at 1year follow-up, it will be at the discretion of the Investigator to follow-up if fusion can be observed at 24 months (only if standard of care at the site)).
  - Spinopelvic alignment parameters (only required for deformity subjects)

In case the patient is symptomatic at 24 months and receives a CT-scan or X-ray, stabilization of pedicle screw instrumentation and fusion status (for those subjects where fusion is intended) will be assessed.

Every attempt should be made to complete the required onsite clinic visit. However, if a subject is unable to complete an onsite visit at 3 months or 24 months, a remote visit source document worksheet can be completed by the Investigator/RC to obtain the required data elements.

The following data can be collected remotely using the remote visit source document worksheet:

- Medication
- VAS back and leg pain conducted by phone or via web-based application
- EQ-5D-5L phone version or via web-based application
- ODI phone version or via web-based application
- Adverse events and/or device deficiencies

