## **5.2 Endpoints**

#### 5.2.1 Primary Endpoint

The primary endpoint is the improvement in ODI at 12 months compared to baseline.

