## 9.7 Recording Data

The Investigator must ensure accuracy, completeness and timeliness of the data reported in the eCRFs and in all other required reports. Data reported on the eCRFs must be consistent with the source documents, and discrepancies need to be justified in a documented rationale, signed and dated by the Investigator, and filed in the subject medical file or appropriate location.

Patient neurological status can be recorded directly on the eCRF and is considered source data. All other source data entered in the eCRFs should be located in the subject's medical records/source document (electronic or paper), (e.g., hospital records, surgery reports, x-rays, MRIs, CTs, or any other material that contains original information used for data collection including the documentation of AEs

#MDT17040SD1703

and study source document completed by the Investigator or site staff). Subject completed questionnaires as well as data collected during subject phone calls will be considered as source data.

This study will be conducted using a remote data capture system. The Oracle Clinical Remote Data Capture (RDC) system allows the study centers to enter study data into the sponsor's database over a secure internet connection. Required data will be taken from source documents and directly entered into the study database by authorized site personnel in accordance with applicable regulations.

Every attempt should be made to complete the required onsite clinic visit. However, if the subject is unable to return to the investigational site for their scheduled clinic visit at 3 months and 24 months, the study site can contact the subject and collect the following data remotely using the remote visit source document worksheet:

- Medication
- VAS back and leg pain conducted by phone or web-based application
- EQ-5D-5L phone version or web-based application
- ODI phone version or web-based application
- Adverse events and/or device deficiencies

The Principal Investigator or an individual delegated by the Principal Investigator on the Delegation of Authority Log, is responsible for documenting and entering data for the study on the eCRFs. Only authorized persons can complete CRFs. CRFs shall be signed by Principal or Sub-Investigators

(physicians only) as specified on the Delegation of Authority Log included in the Investigator Site File. The Principal Investigator or delegated Sub-Investigator is required to approve all data on CRFs via electronic signature.

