## 9.9 Subject Withdrawal or Discontinuation

Subjects are free to voluntarily withdraw from the study at any time and for any reason. The Investigator can only withdraw a subject from the study with a valid reason. Withdrawn or exited subjects will be followed under normal medical practice. Examples of reasons for subject discontinuation include, but are not limited to, those listed below:

- Patient Informed Consent procedure not followed
- Subject does not meet all eligibility criteria
- Subject death
- Subject lost to follow-up
- Subject voluntarily withdraws from the study
- Subject did not undergo the fenestrated screw procedure as defined in this protocol

If a subject is withdrawn from the study, the reason for withdrawal (if known) shall be recorded in the eCRF and in the subject's hospital record.

Subjects withdrawn from the study will only be replaced when subjects did not meet baseline eligibility or did not undergo the fenestrated screw procedure as defined in this protocol and if the enrollment is still open.

Compliance to the minimum recommended follow-up schedule is essential to enable the analysis of the results in a scientifically sound and meaningful way. If, for whatever reason, the subject follow-up cannot be scheduled within the time window or occurred outside the time window, it is still essential to schedule a follow-up visit and to document the subject data at a date as close as possible to the calculated follow-up date.

As much as possible, it should be avoided that subjects are lost-to-follow-up and Investigators are urged to do their utmost best to maintain patient's follow-up compliance as per CIP.

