## 13.3 Analysis Dataset

All the analysis will be based on the primary dataset which consists of all subjects who are enrolled in this study, undergo the intended surgical procedure and receive the study device. The per-protocol dataset, which excludes from the primary dataset all subjects who violate inclusion/exclusion criteria may also be derived in the case there are a meaningful number of major protocol deviations.

Subjects from all sites will be pooled together. The analysis will be based on the observed data. Missing data will not be imputed.

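### The remote fallback for questionnaires covers the 3- and 24-month visits but omits 12 months, which leaves avoidable missing data in the primary endpoint

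*Protocol*

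**What the plan says.** CIP 5.2.1 fixes the primary endpoint: "The primary endpoint is the improvement in ODI at 12 months compared to baseline". CIP 9.1.5 asks sites to try for an on-site visit each time, then permits a remote worksheet "if a subject is unable to complete an onsite visit at 3 months or 24 months". CIP 9.7 gives the same permission in slightly different words: "if the subject is unable to return to the investigational site for their scheduled clinic visit at 3 months and 24 months". Both sections list the same remote items: medication, VAS back and leg pain, EQ-5D 5L, ODI, and adverse events or device deficiencies. For the primary instrument the entry in CIP 9.1.5 reads "ODI phone version or via web-based application". Neither section mentions 12 months.

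The 12-month visit carries extra content. The passage that begins "The post-operative assessment at 12 months also includes" adds a neurological examination and radiologic evaluation of screw stabilization, of fusion where intended and, in deformity subjects, of spinopelvic alignment.

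For visits that cannot be held on time, CIP 9.9 says "it is still essential to schedule a follow-up visit and to document the subject data at a date as close as possible" to the calculated one. CIP 13.3 settles the handling of gaps: "The analysis will be based on the observed data. Missing data will not be imputed". SAP v2.0, sections 7.1.3 and 7.4, keeps that rule.

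**The concern.** The only follow-up visit without a remote route is the one that supplies the primary endpoint. The need for imaging and an examination explains why that visit should be on site by default. It does not explain why the questionnaires should go uncollected when a subject cannot attend, since the CIP accepts phone or web ODI, compared with the same baseline, at the other two visits.

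The stake is missing primary data that an existing worksheet could have captured. The analysis is a single-arm test of mean improvement on observed scores, so a missing score is simply left out. If ability to travel is related to disability, which is what ODI measures, those left out may differ from those who remain. A smaller consequence is that CIP 6.2 uses the 24-month patient-reported outcomes to confirm that the 12-month ones hold, yet the 24-month set can include remote responders whom the 12-month set lacks.

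**Working it through.** **1. The visits side by side (CIP Table 9-1, 9.1.5, 9.7).**

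| Visit | Role of ODI | Required on-site-only items | Remote ODI permitted |
|---|---|---|---|
| 3 months | secondary | none | yes |
| 12 months | primary | neurological examination, imaging | not stated |
| 24 months | secondary | none (imaging conditional) | yes |

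**2. Does another provision fill the gap?**

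- The 12-month window is ±3 months (CIP 9.1.5). This helps a subject whose difficulty is temporary.
- CIP 9.9 asks for a visit, and its data, even outside the window. Again this helps a delayed subject, but no remote mode is named.
- CIP 9.9.2 requires at least three contact attempts before a subject is called lost, aimed at getting the subject to return. The site may thus be speaking to the subject without a stated route to take the ODI.
- CIP 9.7 accepts phone-call data as source data in general, but its list of remotely collectable items is tied to 3 and 24 months.

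The gap that remains is the subject who cannot attend on site at all.

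**3. The plan's sample size.** Inputs from CIP 13.2: mean improvement 10, SD 24, alpha 0.05, power 80%, attrition 20%. The test is taken as one-sided, from the alternative hypothesis in CIP 13.1 and the explicit statement in SAP 7.9.1.

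Power(n) = P(T > t(0.95, n−1)), where T is noncentral t with n−1 degrees of freedom and noncentrality (10/24)·√n.

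- n = 37: 0.79997. n = 38: 0.8095. The smallest n that reaches 80% is 38.
- 38/(1 − 0.20) = 47.5, rounded up to 48.

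Both stated figures, 38 and 48, reproduce.

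**4. Power against total 12-month ODI loss.** The documents give no rate of missed 12-month visits, so these loss rates are assumptions. Enrolment is 48 per indication.

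| Total loss | n with 12-month ODI | Power |
|---|---|---|
| 0% | 48 | 0.885 |
| 10% | 43 | 0.852 |
| 20% | 38 | 0.810 |
| 25% | 36 | 0.790 |
| 30% | 33 | 0.757 |
| 40% | 28 | 0.693 |

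The plan tolerates 48 − 38 = 10 missing per indication from all causes. Near n = 38, each recovered ODI adds 0.8095 − 0.79997 = 0.0096, about one percentage point of power.

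**5. Possible bias.** Let m be the fraction of subjects with no 12-month ODI solely because they could not attend, and let d_obs and d_miss be the mean improvements of those seen and not seen. Then

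observed mean − full mean = m·(d_obs − d_miss).

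Take d_obs = 10, the CIP's planning value. The values of m and d_miss are assumptions, with d_miss placed symmetrically around 10.

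| m | d_miss = 0 | d_miss = 10 | d_miss = 20 |
|---|---|---|---|
| 0.10 | +1.0 | 0 | −1.0 |
| 0.20 | +2.0 | 0 | −2.0 |

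The documents fix neither m nor d_miss, so both the size and the sign are open.

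**The case against.** The best defence is that 12 months is the only follow-up visit with mandatory imaging and examination, and that four kinds of secondary endpoint depend on attendance: neurological success, screw stabilization, fusion and, in deformity subjects, alignment. A remote option could weaken the pressure to attend, and it would mix collection modes in the primary endpoint. This stands as a reason to keep the on-site visit as the default, and as a real though small cost of a fallback. It does not justify having no questionnaire route for someone who will not attend in any case.

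It is also fair that the CIP omits 12 months from a permission and does not prohibit remote ODI, and that the window and CIP 9.9 rescue temporary non-attendance. Neither CIP 13.3 nor SAP 7.1.3 says that an out-of-window ODI is excluded. The endpoint is therefore lost only when no on-site visit takes place.

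Three stronger readings are tempting, and the documents do not support them.

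- *Adverse events and secondary surgeries are lost.* CIP 9.5.2, 9.5.3, 11 and 11.2 collect these continuously from the start of the procedure, and secondary surgeries are captured even when done at another hospital. A missed visit may delay their capture but does not lose them by design.
- *The estimated improvement is biased upward.* The endpoint is change from baseline, so a subject too disabled to travel may have started worse and need not have improved less. An upward bias appears only if a low improvement is assumed for those not seen.
- *The trial becomes underpowered.* The 20% allowance already covers some of this loss, and nothing shows that total loss would exceed it.

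**Conclusion.** The gap is real and appears in two sections, so it is not a slip in one sentence. A subject who cannot attend at all at 12 months has no stated route to provide the primary outcome, although the tools exist and are accepted at 3 and 24 months. The result is avoidable missingness in the primary endpoint, and it may be informative if inability to travel is related to disability. That link is plausible but is not documented in the CIP.

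Its frequency, size and direction cannot be derived from the documents. Power stays at 0.810 at the planned 20% loss and falls below 80% only when more than 10 of 48 per indication are missing; at n = 37 it is 80% to within rounding.

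The effect on the analysis now planned is small. SAP v2.0 follows subjects mainly to 3 months, where a remote route exists. It lists its objectives without a primary one (section 4) and expects two subjects to complete 12 months (section 7.1.1). SAP 7.9.1 still summarises and tests 12-month ODI, so one missed visit would be 1 of 2, but two subjects support no useful inference either way. The point is a low-cost improvement to the CIP design.

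**What to change.** In CIP 9.1.5 and 9.7, extend the remote fallback for the items already listed to the 3-, 12- and 24-month visits. Keep the on-site visit as the default at 12 months, with the remote route reserved for subjects who cannot attend. When a 12-month visit is remote, record imaging and neurological status as assessments not performed, a deviation type that CIP 9.8 already has. Add a variable for the mode of collection, so that 12-month ODI can be summarised with and without remote scores. The change concerns data collection only.

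The worksheet and the phone and web instruments exist, so the operational cost is low. The change still needs a CIP amendment: ethics committee submission, approval before use unless it counts as purely administrative or logistical (CIP 15.7), and investigator signature (CIP 9.8.3). The remaining costs are some mixing of modes in the primary endpoint and perhaps slightly fewer on-site 12-month visits. In a study that is closing at six sites with two 12-month completers expected, the sponsor may reasonably judge that an amendment is not worthwhile now; the wording should be corrected in any later protocol built on this one.
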